9.3.9. Tolerability

The investigator's designee will administer a questionnaire to participants (or parents/guardians) to assess potential side effects of study drug (blurred vision, burning/stinging, eye pain, grittiness in eye, sensitivity to light, headache) with severity scored on a 0 to 3 scale (none, mild, moderate, severe) and frequency indicated as Intermittent or Continuous. The number and percentage of participants for each level of response for each parameter will be summarized at each visit based on current treatment.

The frequency distribution of severity score by visit will be presented by a bar chart.

The instructions to study investigators regarding tolerability assessments and adverse event reporting was inconsistent during the study duration. Only tolerability assessments that were reported as moderate or severe were required to be reported as an AE. Tolerability assessments that were mild were not to be considered AEs. However, some investigative sites were instructed to report any tolerability assessment greater than none as an AE. Investigators were not asked to remove adverse events once reported.

To investigate the potential reporting bias from incorrect site instructions, participants who have an adverse event for selected preferred terms will have their maximum tolerability severity score while on the same treatment as date of ae onset for corresponding assessment summarized.

[Table 9-1](#) below summarizes the assessments to be summarized and the AE preferred terms to define subset for summary. Reported Adverse events will be reviewed as the study progresses and terms to be included for each assessment will be updated as needed.

Table 9-1 Selected Preferred Terms for Tolerability

Assessment	AE Preferred Terms
Blurred Vision	VISION BLURRED, VISUAL ACUITY REDUCED
Burning/Stinging	EYE IRRITATION, OCULAR DISCOMFORT
Eye Pain	EYE PAIN, INSTILLATION SITE PAIN
Grittiness in Eye	FOREIGN BODY SENSATION IN EYES
Sensitivity to Light	PHOTOPHOBIA
Headache	HEADACHE, MIGRAINE, MIGRAINE WITH AURA, TENSION HEADACHE

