4 STUDY DESIGN

4.1 OVERALL DESIGN

The clinical hypotheses for this study are as follows:

- SYD-101 is safe as assessed by the incidence and severity of AEs compared with Vehicle
- SYD-101 is superior to Vehicle in slowing the progression of myopia
 - For European Medicines Agency (EMA) submission, the primary assessment of myopia progression will be assessed by the mean annual progression rate of myopia
 - For US Food and Drug Administration (FDA) submission, the primary assessment of progression will be assessed by the proportion of participants with an increase in myopia >0.75 D

This is a Phase 3, multicentered, randomized, double-masked, vehicle-controlled study to assess the safety and efficacy of SYD-101 eyedrops in male and female children between 3 and 14 years of age (inclusive) with myopia of 0.50 D to 6.00 D (inclusive).

The study will have 3 treatment groups: SYD-101 0.01%, SYD-101 0.03%, and the Vehicle of SYD-101. Each night at bedtime, 1 drop of masked study drug will be instilled in each eye. See [Section 1.2](#) for the figure describing the treatment assignments.

- **Baseline Randomization.** At Baseline, participants will be randomly assigned into 1 of 3 treatment arms, with participants allocated in a 1:1:1 ratio to receive either SYD-101 0.01%, SYD-101 0.03%, or Vehicle during Part 1 (Primary Treatment Period). Allocation to the treatment groups will be stratified according to the following 2 factors: baseline SE and age (see [Section 6.3](#) for stratification details). Enrollment thresholds may be utilized to limit the number of participants in each level of demographic characteristic such as age group, baseline SE group, race, etc. These thresholds will be defined within the interactive voice response system (IVRS)/interactive web response system (IWRS) and may be modified during the course of the study.
- **Re-randomization.** At Month 36, participants will be randomly assigned to receive study treatment during Part 2 (Randomized Withdrawal Period) as follows:
 - Those initially assigned to the SYD-101 0.01% arm will be re-randomized in a 1:1 ratio to receive either masked SYD-101 0.01% or Vehicle
 - Those initially assigned to the SYD-101 0.03% arm will be re-randomized in a 1:1 ratio to receive either masked SYD-101 0.03% or Vehicle

- Those initially assigned to the Vehicle arm (not on escape medication) will be re-randomized to receive masked SYD-101 0.03%

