8.3.5 ADVERSE EVENT REPORTING

All AEs reported or observed during the study will be recorded on the AE page in the eCRF.

Information to be collected includes the following:

- Drug treatment
- Dose
- Event term
- Time of onset
- Investigator-specified assessment of severity and relationship to study drug
- Time of resolution of the event
- Seriousness
- Any required treatment or evaluations
- Outcome

Adverse events resulting from concurrent illnesses, reactions to concurrent illnesses, reactions to concurrent medications, or progression of disease states must also be reported. All AEs will be followed to adequate resolution. The Medical Dictionary for Regulatory Activities (MedDRA) will be used to code all AEs.

Any medical condition that is present at the time that the participant is screened but does not deteriorate should not be reported as an AE. However, if it deteriorates at any time during the study, it should be recorded as an AE.

The following are special considerations when determining and reporting AEs:

- Whenever possible, the investigator should group signs or symptoms that constitute a single diagnosis under a single AE term (eg, “cough, rhinitis, and sneezing” might be grouped together as “upper respiratory tract infection”)
- Any item from the Tolerability Questionnaire with a severity of moderate or severe is to be recorded as an AE
- Corneal staining with a severity of 2 or 3+ is to be recorded as an AE; if other signs or symptoms are present, a diagnosis, such as keratitis, should be recorded
- Progression of myopia, which is collected as a clinical efficacy variable and assessed as unequivocally associated with the disease progression and/or lack of efficacy, should not be reported as an AE unless progression is greater than anticipated in the natural course of the disease
- Any item from the Tolerability Questionnaire with a mild severity is not considered as an AE
- Corneal staining with a severity of 0.5 or 1+ is not considered as an AE
- Small changes in pupil diameter should not be reported as an AE, however, the pursuant symptoms such as photophobia may be an AE

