9.1. Adverse Events

Treatment-emergent AEs are defined as those AEs or SAEs that occur after the start of study drug dosing. All TEAEs will be summarized by treatment group (SYD 101 0.01%, SYD 101 0.03%, or Vehicle) according to treatment taken at the time of event. Adverse events with onset set more than 30 days from date study treatment discontinuation will be summarized separately. In addition, all SAEs, including deaths, will be listed and summarized separately.

For the purpose of inclusion in TEAE tables, incomplete AE start and end dates will be imputed as follows:

Missing onset dates (where UK and UKN indicate unknown or missing day and month respectively):

- UK-MMM-YYYY: If the month and year are different from the month and year of the date of first dose, assume 01-MMM-YYYY. If the month and year are the same as the month and year for the date of first dose, and the end date (after any imputation) is on or after the date of first dose, then assume the date of first dose (Day 1). If the month and year are the same as the date of first dose, and the end date (after any imputation) is prior to the date of first dose, then assume the end date for the start date.
- DD-UKN-YYYY/UK-UKN-YYYY: If the year is different from the year of the date of first dose, assume 01-JAN-YYYY of the collected year. If the year is the same as the date of first dose year, and the end date (after any imputation) is on or after the date of first dose, then assume the date of first dose (Day 1). If the year is the same as the date of first dose, and the end date (after any imputation) is prior to the date of first dose, then assume the end date for the start date.

Missing end dates (where UK and UKN indicate unknown or missing day and month respectively):

- UK-MMM-YYYY: Assume the last day of the month;
- DD-UKN-YYYY/UK-UKN-YYYY: Assume 31-DEC-YYYY

All adverse events will be classified by System Organ Class and Preferred Term (PT) according to the Medical Dictionary for Regulatory Activities (MedDRA, Version 21.0 or higher).

An overview summary of the number and percentage of participants with any TEAE, serious TEAE, treatment-related TEAE, treatment-related serious TEAE, TEAE leading to drug withdrawal, TEAE leading to study discontinuation, and AE leading to death will be provided by treatment group. The overall summaries will be presented for all adverse events, all ocular events, and all non-ocular events.

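### SAP 9.3.9 admits that some sites over-reported mild tolerability scores as AEs, but its one check on this does not compare sites by instruction and no supportive AE table under a single threshold is planned

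*SAP*

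**What the plan says.** Protocol 8.3.5 has moderate and severe questionnaire items recorded as AEs and excludes mild ones: "Any item from the Tolerability Questionnaire with a mild severity is not considered as an AE". SAP 9.3.9 restates the rule ("Only tolerability assessments that were reported as moderate or severe were required to be reported as an AE") and then reports that it was not followed everywhere: "some investigative sites were instructed to report any tolerability assessment greater than none as an AE". The extra records remain: "Investigators were not asked to remove adverse events once reported".

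The response is one summary. The SAP writes "To investigate the potential reporting bias from incorrect site instructions, participants who have an adverse event for selected preferred terms", and says that these children "will have their maximum tolerability severity score while on the same treatment as date of ae onset" summarised for the matching questionnaire item. SAP Table 9-1 pairs the six items with AE preferred terms. The AE onset date selects the treatment, not the questionnaire visit. Nothing in the paragraph separates sites by the instruction they were given.

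The AE tables take the records as they stand. SAP 9.1: "All TEAEs will be summarized by treatment group (SYD 101 0.01%, SYD 101 0.03%, or Vehicle) according to treatment taken at the time of event". SAP 9.1.1 counts a participant once at each level (any AE, organ class, preferred term).

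Two other planned outputs bear on the point. SAP 9.3.9 tabulates every response level of every item at each visit by current treatment. SAP 9.1.1 and 9.1.3 tabulate treatment-emergent AEs (TEAEs) by severity.

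**The concern.** The first clinical hypothesis in Protocol 4.1 is that "SYD-101 is safe as assessed by the incidence and severity of AEs compared with Vehicle". The Table 9-1 terms include blurred vision, photophobia and headache, which Protocol Section 3 names among the potential side effects of the study drug. With two reporting thresholds in use, the as-reported incidence of these terms is a mixture. So is the overall and related TEAE incidence that contains them. The mixing weight is the share of children at wrongly instructed sites, which the documents do not give.

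A reader of the study report will want to know how much of the incidence, and of the difference from Vehicle, comes from the wrong instruction. The planned summary pools all sites, so it has no correctly instructed group to compare with. Separately, where the unit is the event and not the child, a maximum over all time on treatment can lift a mild-triggered AE into the moderate row.

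**Working it through.** The plan gives no figure for this bias, so there is none to reproduce.

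**Step 1: is the maximum the right score for participant incidence?** Take a child with mild photophobia at Month 3, recorded as an AE, and moderate photophobia at Month 30 on the same treatment. Under Protocol 8.3.5 the Month 30 score must itself be an AE. Under SAP 9.1.1 the child counts once for photophobia. The child therefore belongs in the Month 36 count, and showing the maximum as moderate is correct. A child whose maximum is none or mild had no score that required an AE, and the summary shows that too.

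**Step 2: where the maximum can understate over-reporting.** Event totals (SAP 9.1.1 to 9.1.3) and the annual-period summary (SAP 9.1.6) depend on which event was recorded and when. The maximum can equal or exceed the score behind the AE but never fall below it, so the error runs one way.

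- Number of questionnaires k: my reading of the Schedule of Activities row, which is imperfect in the text version. Months 3, 6, 12, 18 and 24 give k = 5 by Month 24; Months 30 and 36 make k = 7.
- The score that triggered the AE is mild by definition, so only the other n = k − 1 visits can raise the maximum: n = 4 and n = 6.
- q is the chance of a moderate or severe score at each other visit. It is an assumption (2%, 5%, 10%); the documents give no rate.

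With independent visits, the share lifted is 1 − (1 − q)^n. For q = 5% and n = 6 this is 1 − 0.95^6 = 1 − 0.7351 = 0.2649.

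With child-specific probabilities drawn from a beta distribution with mean q and within-child correlation 0.5 (beta parameters q and 1 − q), the share is 1 − ∏(1 − q/j) for j = 1 to n. For q = 5% and n = 6 this is 1 − 0.883 = 0.117.

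| Assumed q | Month 24, independent | Month 36, independent | Month 24, correlation 0.5 | Month 36, correlation 0.5 |
|---|---|---|---|---|
| 2% | 8% | 11% | 4% | 5% |
| 5% | 19% | 26% | 10% | 12% |
| 10% | 34% | 47% | 19% | 22% |

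The remaining mild-triggered AEs stay visible as such.

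**Step 3: what two thresholds can do to the comparison with Vehicle.** Let h be the moderate-or-severe incidence, m the mild-only incidence, and s the share of children at wrongly instructed sites. As-reported incidence is h + s·m. All values below are assumed, for illustration only.

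- h = 5% active, 3% Vehicle; m = 20% and 10%. At s = 0 the difference is 2 points. At s = 0.5 it is (5 + 10) − (3 + 5) = 7 points.
- Same h, m = 15% in both arms. At s = 0.5 the difference is 12.5 − 10.5 = 2 points, as at s = 0, but the ratio falls from 5/3 = 1.67 to 12.5/10.5 = 1.19.

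The difference may widen or the ratio may be diluted; which applies depends on data not in the documents.

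**Step 4: do the other tables isolate the effect?** The by-visit questionnaire table does not depend on the AE instruction, but it does not say what AE incidence would be under one rule. The severity tables separate mild events, but mix wrongly reported mild symptoms with mild AEs reported legitimately, and they use the investigator severity definition (Protocol 8.3.3.1) and not the 0 to 3 questionnaire score. Neither is split by instruction.

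**The case against.** The strongest case against the point is that the SAP chose the right score and already shows enough. The maximum on the same treatment matches how SAP 9.1 and 9.1.1 attribute and count participants. The by-visit questionnaire table covers all children whatever their site was told, and the moderate and severe rows of the TEAE tables come close to a single threshold. AE comparisons are descriptive and allocation is masked. Scoring at onset has its own fault: an AE that starts mild and worsens is valid, Protocol 8.3.4 has such changes documented, and SAP 9.1.3 reports the most extreme severity.

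Most of this stands. A reader might infer that the maximum hides the over-reported AEs, or that it is the reason the AE comparison is left uncorrected. The documents support neither. For participant incidence the maximum gives the right answer. At event level it masks an AE only when the same child also scored moderate or severe on that item at another visit on that treatment. The mixed-threshold tables come from having no supportive AE table, and changing the score alone would leave them as they are.

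A further objection is practical. SAP 9.3.9 describes the instructions as inconsistent over the course of the study and names no sites, so timing may matter as well as site, and a split may not be fully possible. That is a fair limit on the fix. What the objection does not answer is that no planned output separates the effect of the wrong instruction from the effect of treatment.

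**Conclusion.** The point holds as a cheap improvement. By the SAP's own account, as-reported incidence of the Table 9-1 terms, and the overall and related TEAE incidence that includes them, mixes two thresholds, and the only check aimed at this does not compare sites by instruction. The maximum is acceptable for participant incidence. For event counts and timing it can understate over-reporting by the shares in the table above, which rest on assumed rates and on my reading of the visit schedule; they are not estimates for this trial.

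A reader might also infer that the wrong instruction biases the comparison against, or in favour of, SYD-101. The documents do not support a direction. Within a masked site the same instruction presumably applied to all arms, and Step 3 shows that the risk difference can widen or stay unchanged while the ratio shrinks. Without the number of affected sites or the score frequencies, the actual size cannot be computed.

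**What to change.** In SAP 9.3.9:

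1. Keep the planned maximum-score summary. State that it is shown by treatment arm (already the default in SAP Section 4) and by site instruction, and by period where a site's instruction changed.
2. Add one supportive table of participant incidence of the Table 9-1 terms by arm, beside the as-reported incidence: (a) under a uniform rule, counting a child with a listed AE if the maximum matching score or the recorded AE severity is moderate or worse; (b) as reported, for correctly instructed sites only, where they can be identified.
3. Say in a footnote that column (a) is a moderate-or-worse incidence. It also drops mild AEs that were reported legitimately, so it is not an estimate of what correct instructions would have produced.

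Matching each AE to the questionnaire nearest its onset, and counting moderate or severe scores with no corresponding AE, are optional.

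The cost is a few lines of SAP text and one table from AE and questionnaire data already collected. Two incidence figures for the same terms will have to be explained, and the site split depends on sponsor records identifying the affected sites and dates. If they cannot, items 2(a) and 3 can still be done, and the report should say why the split is missing.

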9.4. Pregnancy Test

Serum pregnancy testing will be performed on an annual basis using human chorionic gonadotropin pregnancy urine dipstick test (female participants of childbearing potential only.) Pregnancy testing results will be listed.

10. Interim Analysis

There are no interim analyses planned for this study. Analyses performed at Month 24 for the EMA Submission are considered the final analysis of primary efficacy for that submission. Analyses performed at Month 36 for the FDA Submission are considered the final analysis of primary efficacy for that submission.

11. Changes in Planned Analysis

With protocol amendment 3, intercurrent event analysis has been expanded to include 6 sensitivity analyses per FDA and EMA primary and key secondary efficacy endpoint and the intercurrent event approaches for all endpoints have been modified from original protocol incorporating regulatory feedback from the FDA and EMA. An additional subgroup for fast-progressors has been added to the EMA endpoint to be included in secondary analysis. Statistical testing will be performed for QOL assessments for informational purposes.

12. Impact of COVID-19 on the Planned Analyses

On January 31, 2020, the Department of Health and Human Services issued a declaration of a public health emergency related to the Coronavirus Disease 2019 (COVID-19) acute respiratory disease, and on March 13, 2020, the President declared a national state of emergency. The Food and Drug Administration has recognized that the COVID-19 pandemic may impact the conduct, evolution, and statistical analyses of clinical trials across therapeutic areas (March and June 2020). Participants with missing clinic visits due to COVID-19 will be listed; participants were able to complete questionnaires via phone.

14. APPENDICES

14.1. Summary of Analyses including Primary, Key Secondary, Secondary and Sensitivity

Analysis	Intercurrent Events					
	Intermittent Missing Data	Receipt of Prohibited Treatment	Receipt of Escape Therapy	Treatment Discontinuation	Study Discontinuation	Invalid SE Values
Primary Analysis	Hypothetical	EMA Endpoint: While on Treatment	EMA Endpoint: While on Treatment	EMA Endpoint: Hypothetical	EMA Endpoint: Hypothetical	Treatment Policy
FAS While on Treatment/ Hypothetical	Multiple imputation assuming MAR	MMRM using observed data until receipt of prohibited treatment (no multiple imputation)	MMRM using observed data until receipt of escape medication (no multiple imputation)	Observations after discontinuation (DC) due to a related AE will be multiply imputed assuming MNAR using a sequential vehicle-based pattern regression	Observations after discontinuation (DC) due to a related AE will be multiply imputed assuming MNAR using a sequential vehicle-based pattern regression	Use observed data
EMA Endpoint is Annualized Progression Rate at Month 24		FDA Endpoint: Composite	FDA Endpoint: Composite	Observations after Treatment DC for other reasons will be multiply imputed assuming MAR	Observations after DC for other reasons will be multiply imputed assuming MAR	
FDA Endpoint is Confirmed Progression at Month 36		Participants who receive of prohibited treatment will be considered non-responders (e.g., have progressed)	Participants who receive escape medication will be considered non-responders (e.g., have progressed)	FDA Endpoint: Composite	FDA Endpoint: Composite	
				Participants with discontinuation (DC) due to a related AE are non-responders	Participants with discontinuation (DC) due to a related AE are non-responders	
				Observations after DC for other reasons will be multiply imputed assuming MAR	Observations after DC for other reasons will be multiply imputed assuming MAR	

Analysis	Intercurrent Events					
	Intermittent Missing Data	Receipt of Prohibited Treatment	Receipt of Escape Therapy	Treatment Discontinuation	Study Discontinuation	Invalid SE Values
Key Secondary	Hypothetical	EMA Endpoint: Composite	EMA Endpoint: Composite	Hypothetical	Hypothetical	Treatment Policy
FAS Multiple Imputation/ Composite	Multiple imputation assuming MAR	Participants who receive prohibited treatment will be considered non-responders	Participants who receive escape medication will be considered non-responders	Observations after discontinuation (DC) due to a related AE will be multiply imputed assuming MNAR using a sequential vehicle-based pattern regression	Observations after discontinuation (DC) due to a related AE will be multiply imputed assuming MNAR using a sequential vehicle-based pattern regression	Use observed data
EMA Endpoint is Confirmed Progression Annualized Progression Rate at Month 24		FDA Endpoint: Hypothetical	FDA Endpoint: Hypothetical	Observations after Treatment DC for other reasons will be multiply imputed assuming MAR	Observations after DC for other reasons will be multiply imputed assuming MAR	
FDA Endpoint is Annualized Progression Rate at Month 36		Observations after receipt of prohibited treatment will be multiple imputed assuming MNAR; using a sequential vehicle-based pattern regression	Observations after receipt of escape medication will be multiple imputed assuming MNAR; using a sequential vehicle-based pattern regression			
Secondary Endpoints	Hypothetical	Hypothetical	Hypothetical	Hypothetical	Hypothetical	Treatment Policy
FAS Multiple Imputation	Multiple imputation assuming MAR	Observations after receipt of prohibited treatment will be multiple imputed assuming MAR	Observations after receipt of escape medication will be multiple imputed assuming MAR	Observations after discontinuation (DC) due to a related AE will be multiply imputed assuming MNAR using a sequential vehicle-based pattern regression	Observations after discontinuation (DC) due to a related AE will be multiply imputed assuming MNAR using a sequential vehicle-based pattern regression	Use observed data
Same methodology employed at Month 24 and Month 36 for any secondary endpoints derived from SE				Observations after Treatment DC for other reasons will be multiply imputed assuming MAR	Observations after DC for other reasons will be multiply imputed assuming MAR	

Analysis	Intercurrent Events					
	Intermittent Missing Data	Receipt of Prohibited Treatment	Receipt of Escape Therapy	Treatment Discontinuation	Study Discontinuation	Invalid SE Values
Secondary Endpoints	Hypothetical	Hypothetical	Hypothetical	Hypothetical	Hypothetical	Treatment Policy
PPS Multiple Imputation Same methodology employed at Month 24 and Month 36 for any secondary endpoints derived from SE	Multiple imputation assuming MAR	Observations after receipt of prohibited treatment will be multiple imputed assuming MAR	Observations after receipt of escape medication will be multiple imputed assuming MAR	Observations after discontinuation (DC) due to a related AE will be multiply imputed assuming MNAR using a sequential vehicle-based pattern regression Observations after Treatment DC for other reasons will be multiply imputed assuming MAR	Observations after discontinuation (DC) due to a related AE will be multiply imputed assuming MNAR using a sequential vehicle-based pattern regression Observations after DC for other reasons will be multiply imputed assuming MAR	Use observed data
Sensitivity Analysis 1 PPS Primary Efficacy Endpoints While on Treatment/ Hypothetical EMA Endpoint is Annualized Progression Rate at Month 24 FDA Endpoint is Confirmed Progression at Month 36	Hypothetical Multiple imputation assuming MAR	EMA Endpoint: While on Treatment MMRM using observed data until receipt of prohibited treatment (no multiple imputation) FDA Endpoint: Composite Observations after receipt of prohibited treatment will be considered non-responders (e.g., have progressed)	EMA Endpoint: While on Treatment MMRM using observed data until receipt of escape medication (no multiple imputation) FDA Endpoint: Composite Observations after receipt of escape medication will be considered non-responders (e.g., have progressed)	EMA Endpoint: Hypothetical Observations after discontinuation (DC) due to a related AE will be multiply imputed assuming MNAR using a sequential vehicle-based pattern regression Observations after Treatment DC for other reasons will be multiply imputed assuming MAR FDA Endpoint: Composite	EMA Endpoint: Hypothetical Observations after discontinuation (DC) due to a related AE will be multiply imputed assuming MNAR using a sequential vehicle-based pattern regression Observations after DC for other reasons will be multiply imputed assuming MAR FDA Endpoint: Composite	Hypothetical Multiple imputation assuming MAR

Analysis	Intercurrent Events					
	Intermittent Missing Data	Receipt of Prohibited Treatment	Receipt of Escape Therapy	Treatment Discontinuation	Study Discontinuation	Invalid SE Values
				
Participants with discontinuation (DC) due to a related AE are non-responders
 
Observations after DC for other reasons will be multiply imputed assuming MAR
	
Participants with discontinuation (DC) due to a related AE are non-responders
 
Observations after DC for other reasons will be multiply imputed assuming MAR
	
Sensitivity Analysis 1						
PPS Key Secondary Endpoints	Hypothetical	EMA Endpoint: Composite	EMA Endpoint: Composite	Hypothetical	Hypothetical	Hypothetical
FAS Multiple Imputation/ Composite	Multiple imputation assuming MAR	Participants who receive prohibited treatment will be considered non-responders	Participants who receive escape medication will be considered non-responders	Observations after discontinuation (DC) due to a related AE will be multiply imputed assuming MNAR using a sequential vehicle-based pattern regression	Observations after discontinuation (DC) due to a related AE will be multiply imputed assuming MNAR using a sequential vehicle-based pattern regression	Multiple imputation assuming MAR
EMA Endpoint is Confirmed Progression Annualized Progression Rate at Month 24		FDA Endpoint: Hypothetical	FDA Endpoint: Hypothetical	Observations after Treatment DC for other reasons will be multiply imputed assuming MAR	Observations after DC for other reasons will be multiply imputed assuming MAR	
FDA Endpoint is Annualized Progression Rate at Month 36		Observations after receipt of prohibited treatment will be multiple imputed assuming MNAR; using a sequential vehicle-based pattern regression	Observations after receipt of escape medication will be multiple imputed assuming MNAR; using a sequential vehicle-based pattern regression			
Sensitivity Analysis 2						
FAS Treatment Policy for Prohibited and Rescue Treatments	Hypothetical	Treatment Policy	Treatment Policy	Treatment Policy	EMA Endpoint: Hypothetical	Treatment Policy
EMA Endpoint is Annualized Progression Rate at	Multiple imputation assuming MAR	Use observed data	Use observed data	Use observed data	Observations after discontinuation (DC) due to a related AE will be multiply imputed assuming MNAR	Use observed data

Analysis	Intercurrent Events					
	Intermittent Missing Data	Receipt of Prohibited Treatment	Receipt of Escape Therapy	Treatment Discontinuation	Study Discontinuation	Invalid SE Values
Month 24 and Month 36 FDA Endpoint is Confirmed Progression at Month 24 and Month 36					Observations after Treatment DC for other reasons will be multiply imputed assuming MAR FDA Endpoint: Composite Participants with discontinuation (DC) due to a related AE are non-responders Observations after DC for other reasons will be multiply imputed assuming MAR	
Sensitivity Analysis 3 FAS MAR Tipping Point Add fixed values of c to SYD imputed values	Hypothetical Multiple imputation assuming MAR	Hypothetical Observations after receipt of prohibited medication will be multiply imputed assuming MAR	Hypothetical Observations after receipt of escape medication will be multiply imputed assuming MAR	Treatment Policy Use observed data	Hypothetical Multiple imputation assuming MAR	Treatment Policy Use observed data
Sensitivity Analysis 4 FAS MNAR – exclude prohibited and escape observations before MNAR	Hypothetical Multiple imputation assuming MAR	Hypothetical Observations after receipt of prohibited medication will be multiply imputed assuming MAR	Hypothetical Observations after receipt of escape medication will be multiply imputed assuming MNAR	Treatment Policy Use observed data	Hypothetical Observations after study discontinuation will be multiply imputed assuming MNAR	Treatment Policy Use observed data
Sensitivity Analysis 5 FAS MNAR – include vehicle post prohibited and escape observations	Hypothetical Multiple imputation assuming MAR	Treatment policy for vehicle Use observed data Hypothetical for SYD	Treatment policy for vehicle Use observed data Hypothetical for SYD	Treatment Policy Use observed data	Hypothetical Observations after study discontinuation will be multiply imputed assuming MNAR	Treatment Policy Use observed data

Analysis	Intercurrent Events					
	Intermittent Missing Data	Receipt of Prohibited Treatment	Receipt of Escape Therapy	Treatment Discontinuation	Study Discontinuation	Invalid SE Values
		Observations after receipt of prohibited medication will be multiply imputed assuming MNAR	Observations after receipt of escape medication will be multiply imputed assuming MNAR			
Sensitivity Analysis 6 FAS for confirmed progression only – all missing = progression	Hypothetical Multiple imputation assuming MAR	Hypothetical Observations after receipt of prohibited medication will be multiply imputed assuming MAR	Hypothetical Observations after receipt of escape medication will be multiply imputed assuming MAR	Treatment Policy Use observed data	Composite If participant has missing assessment at Month X and participant discontinued study prior to Month X, a progression will be imputed for Month X regardless of reason for discontinuation Where X = Month 36 for FDA submission, 24 for EMA submission	Treatment Policy Use observed data
Sensitivity Analysis 7 FAS for annual progression rate only – MMRM no imputation	Hypothetical MMRM assumes MAR	Hypothetical Observations after receipt of prohibited medication will be censored. MMRM assumes MAR	Hypothetical Observations after receipt of escape medications will be censored. MMRM assumes MAR	Treatment Policy Use observed data	Hypothetical MMRM assumes MAR	Treatment Policy Use observed data

